7.10. Feasibility of the proposed research

The study material and methods technique are available and feasible in Thumbay Dental Hospital.

7.11. Details of data storage

The data gathered from this research will be securely stored in Thumbay Dental Hospital. Preoperative data for each patient will be recorded in the predetermined patient's chart, which includes age, sex, and tooth number before the treatment.

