7.2. Study population

The study population consists of 60 participants, aged 18–70 years, who will sign the informed consent. The number of participants is chosen according to a previous study (12).

Inclusion criteria

1. Age: 18–70 years
2. A patient diagnosed with symptomatic irreversible pulpitis/acute apical periodontitis
3. require endodontic therapy
4. Mandibular first molars that are diagnosed with symptomatic irreversible pulpitis/acute apical periodontitis
5. Healthy patients without systemic disease
6. Permanent mature first mandibular molars

Exclusion criteria

1. Medically compromised patients

2. Pregnant patients
3. Teeth with incomplete apex formation
4. Teeth with calcified canals
5. Periapical abscess
6. Patients on antibiotic therapy

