7.8. Ethical issues

The proposal will be submitted to the Institutional Review Board of Gulf Medical University Ajman, UAE. After obtaining the approval the research will be conducted. The confidentiality, anonymity, and privacy of the members will be kept up with.

The patient will be asked to sign a printed consent form explaining the aim of the study and to fill the pain scale chart postoperatively at 6, 24, 48, 72 hours, and 7 days, after root canal treatment and return it to the operator at day 8.

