- 10) After completion of cleaning and shaping in group III, 20 ml cryo-treated saline maintained at a temperature of 2°C–4°C will be irrigated for 5 min in each canal.
- 11) All the participants will receive a sheet containing VAS after the procedure. After 6, 24, and 48h, patients are to record the intensity of pain in the area of the root canal (using VAS

from 1 to 10). Analgesic pills that had been taken by the patient are to be recorded on the patient's

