7.12. Data analysis

Data obtained will be tabulated and statistically analyzed by the SPSS software to compare the effect of cryotherapy and occlusal reduction on the level of post-endodontic pain. Patient characteristics will be assessed using numbers, percentages, and mean scores for pain severity. Regarding the type of further statistical test, the decision will be taken later after discussion with the biostatistician regarding the best method for data analysis.

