**NCT number: NCT05722704**

**Official title: Effect of Cryotherapy on Post-endodontic Pain**

**ID: IRB/COD/STD/14/May-2022**

**Date: November 13, 2024**

**Statistical Analysis:**

Categorical data were presented as frequency and percentage values and were analyzed using the chi-square test. Numerical data were presented as mean, standard deviation (SD), median, and interquartile range (IQR) values. They were analyzed for normality using Shapiro-Wilk's test. Age data were normally distributed and were analyzed using one-way ANOVA followed by Tukey's post hoc test. Pain score data were non-parametric and were analyzed using Kruskal-Wallis's test followed by Dunn's post hoc test for intergroup comparisons and Friedman's test followed by Nemenyi post hoc test for intragroup comparisons. Correlations were analyzed using Spearman's rank-order correlation coefficient. The significance level was set at  $p<0.05$  within all tests. Statistical analysis was performed with R statistical analysis software version 4.3.2 for Windows\*.

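### No preoperative pain score is scheduled in the readable plan, so pain before treatment may go unreported by arm and the valid between-group pain test is left unadjusted (minor)

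*Protocol*

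**What the plan says.** **Population.** Protocol 7.2 lists as an inclusion criterion "A patient diagnosed with symptomatic irreversible pulpitis/acute apical periodontitis". It sets no minimum pain score, and the envelope draw in 7.1 and 7.9 is not stratified by pain.

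**Preoperative data.** Protocol 7.11 says the chart is one "which includes age, sex, and tooth number before the treatment". Step 1 of 7.9 adds pulp, mobility, palpation and percussion tests, but no pain rating.

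**Pain measurements.** Protocol 7.8 asks the patient "to fill the pain scale chart postoperatively at 6, 24, 48, 72 hours, and 7 days, after root canal treatment". Step 11 of 7.9 states "All the participants will receive a sheet containing VAS after the procedure" and then lists 6, 24 and 48 h. The two schedules differ, which is a separate matter, but neither contains a mark before treatment.

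**Analysis.** Protocol 7.12 says "Patient characteristics will be assessed using numbers, percentages, and mean scores for pain severity" and leaves the choice of test for later. The SAP then states: "Pain score data were non-parametric and were analyzed using Kruskal-Wallis's test followed by Dunn's post hoc test for intergroup comparisons". The only baseline variable it names is age: "Age data were normally distributed and were analyzed using one-way ANOVA". It also runs Friedman tests within groups, without naming the time points, and adds "Correlations were analyzed using Spearman's rank-order correlation coefficient", without naming the variables.

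**The concern.** In a symptomatic population, pain before treatment is a basic description of the arms and a natural candidate predictor of pain afterwards. Age, sex and tooth number do not tell a reader how much the teeth hurt.

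Two things are at stake:

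- **Reporting.** Without a baseline score, no table can show whether the three arms started from similar pain.
- **Precision.** If baseline pain predicts postoperative pain, a test that ignores it has less power than one that uses it. The sample size is taken from a previous study, with no stated power, effect size or SD (7.3, 7.5), so the plan shows no margin that would make such a loss harmless.

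**Working it through.** **1. Is a preoperative score scheduled?** The places that could schedule one are the chart (7.11), the pre-procedure tests (7.9, step 1), the VAS instructions (7.8; 7.9, step 11) and the SAP. None of them does. Three places leave the question open: 7.11 gives what may be a non-exhaustive list, 7.12 puts mean pain severity beside patient characteristics without a time point, and the SAP does not name the Friedman time points or the Spearman variables. The result is *not specified*, which is weaker than *not collected*.

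**2. Plan's own figure.** 3 arms × 20 = 60 agrees with 7.3. The documents give nothing from which the 60 can be derived, and no figure on baseline pain. Everything below rests on assumptions.

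**3. Chance imbalance in baseline pain at 20 per arm.**
- SE of a difference between two arm means = √(2/20) = 0.316 SD.
- One given pair: P(|difference| > 0.5 SD) = 2 × [1 − Φ(0.5/0.316)] = 2 × [1 − Φ(1.58)] = 0.114.
- Any of the three pairs: 0.254 (2,000,000 simulated trials).

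The test's 5% error rate already allows for this. The figure bears only on what a reader can see.

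**4. Precision, simple approximation.** For a pairwise comparison of means, two-sided 0.05, adjustment multiplies the SD by √(1 − ρ²). With an assumed 0.8 SD difference, power = Φ(0.8/[0.316 × √(1 − ρ²)] − 1.96).
- ρ = 0: Φ(2.53 − 1.96) = 72%.
- ρ = 0.3: Φ(2.65 − 1.96) = 76%.
- ρ = 0.5: Φ(2.92 − 1.96) = 83%.
- ρ = 0.7: Φ(3.54 − 1.96) = 94%.

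This ignores ties and scores at the bottom of the 1–10 scale.

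**5. Precision, simulation on the 1–10 scale.** Assumed shapes: baseline = round(6.5 + 1.8z) and postoperative = round(exp(μ + 0.6w)), both clipped to 1–10, with corr(z, w) = ρ. One arm's w is lowered by 0.8. There are 3 × 20 patients and 40,000 trials per cell, with an overall 2-df test at 0.05. The values μ = 0.9, 0.5 and 0.1 put 30%, 54% and 76% of scores at 1.

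Kruskal-Wallis is shown with its usual chi-square reference and also with the F(2, 57) reference that rank ANCOVA uses. The gain is rank ANCOVA minus Kruskal-Wallis under the common F reference.

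| At floor | ρ | KW, chi-square | KW, F | Rank ANCOVA, F | Gain (points) |
|---|---|---|---|---|---|
| 30% | 0.2 | 64.3% | 65.1% | 66.0% | 0.9 |
| 30% | 0.4 | 64.8% | 65.7% | 71.1% | 5.4 |
| 30% | 0.6 | 65.1% | 65.9% | 80.6% | 14.7 |
| 54% | 0.2 | 54.6% | 55.6% | 55.8% | 0.2 |
| 54% | 0.4 | 54.7% | 55.7% | 59.9% | 4.2 |
| 54% | 0.6 | 55.1% | 56.2% | 68.2% | 12.0 |
| 76% | 0.2 | 34.3% | 35.3% | 35.6% | 0.3 |
| 76% | 0.4 | 34.1% | 35.0% | 37.6% | 2.6 |
| 76% | 0.6 | 33.6% | 34.6% | 41.5% | 6.9 |

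The reference distribution alone is worth 0.8 to 1.1 points, as much as the whole gain at ρ = 0.2 or more. With no shift, all three tests reject in about 4.5% to 5.2% of trials. With a 0.5 SD shift, the gains at ρ = 0.2 / 0.4 / 0.6 are 0.3 / 3.7 / 10.6 points at 26% floor and 0.5 / 1.7 / 3.8 at 74% floor.

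**The case against.** **A score may exist.** Protocol 7.12 can be read as planning a summary of baseline pain severity, and the Friedman or Spearman analyses might use a preoperative mark. The patient chart and VAS sheet are not reproduced, and the readable text of step 11 in 7.9 breaks off mid-sentence. This stands. A reader might infer that baseline pain was never collected, or that reporting it by arm was ruled out. The documents support neither.

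**The unadjusted test is not an error.** Kruskal-Wallis with Dunn is a coherent choice for a bounded score at 20 per arm, and randomisation keeps it valid. This stands too. A reader might infer that chance imbalance biases the comparison or inflates the error rate. The simulation shows neither, and the 25% figure describes visibility only.

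**The gain is assumed and may be small.** At correlation 0.2 it is negligible once both tests use the same reference distribution. It would also be wrong to say that the gain matters only at early time points: at 76% floor and correlation 0.6 it is still about 7 points.

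**It is late.** The SAP is dated November 2024, is written in the past tense and reports normality results, so new collection is probably no longer possible.

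These objections limit the size and urgency. They do not supply a scheduled baseline score or an adjusted analysis.

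**Conclusion.** The point holds as a minor one. No readable section schedules a preoperative pain score, and the between-group pain test uses no covariate. As written, the plan assures neither a description of the arms' pain before treatment nor an analysis that uses it.

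The precision at stake is illustrative. For a 0.8 SD shift in one arm it is about 0 to 1 power points at correlation 0.2, 3 to 5.5 at 0.4 and 7 to 15 at 0.6, and smaller as more scores sit at the floor. These figures rest on assumed score distributions, correlation and effect size, none of which the documents give. The reporting gap does not depend on those assumptions, only on whether a score was charted.

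**What to change.** Clarify in 7.11 and the SAP whether a preoperative VAS was charted, and name the Friedman time points and Spearman variables. Then:

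1. **If a score was charted:** report it by arm. Beside the unadjusted Kruskal-Wallis, add a comparison of postoperative VAS adjusted for it (rank ANCOVA or proportional odds), labelled post hoc.
2. **If collection is still open:** add one pre-anaesthesia VAS mark to the existing sheet and to 7.11, and prespecify the adjusted comparison. Patients already treated cannot supply this mark, so say how they are handled.
3. **If neither applies:** state the missing baseline pain as a limitation.

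**Cost.** With data in hand: one clarifying sentence, plus either a baseline row and one model or one sentence of limitation. With collection open: one extra mark on an existing form and one model.

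**Downsides.** Rank ANCOVA gives a test but no effect in VAS units. Proportional odds gives a conditional odds ratio, and its assumption may be strained by sparse categories at 20 per arm, most of all when most scores sit at the floor.

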7.12. Data analysis

Data obtained will be tabulated and statistically analyzed by the SPSS software to compare the effect of cryotherapy and occlusal reduction on the level of post-endodontic pain. Patient characteristics will be assessed using numbers, percentages, and mean scores for pain severity. Regarding the type of further statistical test, the decision will be taken later after discussion with the biostatistician regarding the best method for data analysis.

**NCT number: NCT05722704**

**Official title: Effect of Cryotherapy on Post-endodontic Pain**

**ID: IRB/COD/STD/14/May-2022**

**Date: November 13, 2024**

**Statistical Analysis:**

Categorical data were presented as frequency and percentage values and were analyzed using the chi-square test. Numerical data were presented as mean, standard deviation (SD), median, and interquartile range (IQR) values. They were analyzed for normality using Shapiro-Wilk's test. Age data were normally distributed and were analyzed using one-way ANOVA followed by Tukey's post hoc test. Pain score data were non-parametric and were analyzed using Kruskal-Wallis's test followed by Dunn's post hoc test for intergroup comparisons and Friedman's test followed by Nemenyi post hoc test for intragroup comparisons. Correlations were analyzed using Spearman's rank-order correlation coefficient. The significance level was set at  $p<0.05$  within all tests. Statistical analysis was performed with R statistical analysis software version 4.3.2 for Windows\*.

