7.3. Sample size calculation

The study will be conducted on 60 patients: with 20 first mandibular molars in each group (n=20). The number of participants is chosen as per a previous study by Western et al. (12).

Group I (control group): normal room temperature saline irrigation protocol without occlusal reduction

Group II (occlusal reduction group): normal room temperature saline irrigation protocol with occlusal reduction

Group III (cryotherapy group): final irrigation with cold saline (2.5C-4C) without occlusal reduction

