7.7. Study instrument & validation procedure

- Post-endodontic pain will be measured by a visual analog scale (VAS) from 1 to 10.
- The temperature of the cold saline should be 2-4 °C. The saline will be placed in a refrigerator with a thermometer sensor to confirm the 2 to 4°C temperature range.
- After removal, the temperature of the cold saline will be preserved by keeping the irrigation syringes in a special box filled with ice with a thermometer.
- The thermometer will be calibrated according to the manufacturer's instructions.

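### With five readings and 20 patients per arm, the SAP's Nemenyi test can have low power for within-arm change between neighbouring readings

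*SAP*

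**What the plan says.** The SAP (Statistical Analysis) treats pain scores as non-parametric. Between arms it uses Kruskal-Wallis and Dunn. Within arms it uses "Friedman's test followed by Nemenyi post hoc test for intragroup comparisons". On the error rate it says "The significance level was set at" p<0.05 for all tests. It does not list the reading times that enter these tests.

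The protocol gives two schedules. Under section 7.8 patients are to "fill the pain scale chart postoperatively at 6, 24, 48, 72 hours, and 7 days", which is five readings. Section 7.9, step 11, has three: "After 6, 24, and 48h, patients are to record the intensity of pain". On the scale, section 7.7 says: "Post-endodontic pain will be measured by a visual analog scale (VAS) from 1 to 10". It therefore has a floor, and tied scores are possible.

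Sections 7.3 and 7.9 put 20 patients in each of three arms. The stated basis is "The number of participants is chosen as per a previous study"; no effect size, SD or power is given.

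**The concern.** Nemenyi ranks all readings within each patient, averages the ranks over patients, and compares each pair of mean ranks with one critical difference. That critical difference depends only on the number of readings and the number of patients. Two consequences follow.

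- A consistent fall between neighbouring readings may move the mean rank by only one place, whatever its size in scale points. With few patients and several readings, one place may not be enough.
- The result for 6 h against 24 h depends partly on what patients mark at 72 h and 7 days, which has no bearing on that comparison.

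At stake is a report of no significant within-arm change between neighbouring readings, such as over the first day, when the change was large and consistent.

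**Working it through.** **Plan's own figure.** The only figure to reproduce is the sample size: 3 × 20 = 60. The formula in protocol section 7.5 is printed without inputs, and the documents give no power for any comparison, so nothing further can be reproduced.

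**Inputs.** n = 20 patients per arm (sections 7.3 and 7.9); k = 5 readings (section 7.8) or k = 3 (section 7.9); alpha 0.05 (SAP). The upper 5% points of the studentized range with infinite degrees of freedom are q = 3.858 for k = 5 and 3.314 for k = 3. The arithmetic assumes no missing marks and the standard Nemenyi form without tie correction.

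**Critical difference (CD).** CD = (q/√2) × √(k(k+1)/(6n)).
- k = 5: (3.858/1.414) × √(30/120) = 2.728 × 0.5 = 1.364.
- k = 3: (3.314/1.414) × √(12/120) = 0.741.

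**Every patient falls at every reading, k = 5.** Mean ranks are 5, 4, 3, 2, 1.
- Friedman: chi-square 80, p about 2 × 10⁻¹⁶.
- Nemenyi, neighbouring readings (gap 1.00): p = 0.27.
- Nemenyi, two readings apart (gap 2.00): p = 0.0006. Three or four apart: p < 0.00001.
- Exact paired test of 20 falls in 20 patients: 2 × 0.5²⁰ = 0.0000019. Multiplied by all 10 pairs of times, the most Holm could do, this is 0.000019.
- Patients needed for a gap of 1.00 to be significant: n ≥ q² × k(k+1)/12 = 3.858² × 30/12 = 37.2, so 38 per arm.

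**Every patient falls at every reading, k = 3.** The gap is again 1.00 but the CD is 0.741, so p = 0.0045.

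**Ties at the floor, k = 5.** A patient at the floor from 24 h onward has ranks 5, 2.5, 2.5, 2.5, 2.5, a 6 h to 24 h gap of 2.5. Mixed with patients who fall at every reading:
- 4 of 20 at the floor: (4 × 2.5 + 16 × 1)/20 = 1.30, p = 0.070.
- 5 of 20: (5 × 2.5 + 15 × 1)/20 = 1.375, p = 0.047.
- 20 of 20: 2.5, p = 0.00001.

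**Simulated power, 6 h against 24 h.** The documents give no pain means or SDs, so all inputs here are assumptions: whole scores 1 to 10, n = 20, between-patient SD 1.5, within-patient SD 1.0. Holm is applied over all pairs of times in the arm.

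| Assumed means, five readings | Nemenyi | Holm signed-rank |
|---|---|---|
| 6, 4.5, 3.3, 2.3, 1.2 (slow) | 3% | 97% |
| 5, 3, 1.5, 1, 1 (faster) | 36% | 100% |
| 4, 2, 1, 1, 1 (early floor) | 77% | 99% |

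On the slow course with within-patient SD 1.5, the figures were about 5% and 58% to 60%. With only three readings they were about 73% and 99% for the slow course, and 97% and 100% for a faster fall. The paired tests had more power for this comparison in every case tried, though the margin was small in the last.

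**The case against.** The strongest reply is that the defect is conditional and lies off the main question.

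A reader might infer from the strict-fall case that Nemenyi can never show a fall between neighbouring readings, and that the trial would report none from 6 h to 24 h in any arm. The documents do not support that. The gap is held at 1.00 only if patients keep falling through 72 h and 7 days. On a bounded scale, five patients in 20 at the floor from 24 h are enough for significance. No expected pain course is given, and power over the assumed courses runs from very low to fairly good. Nor is the five-reading schedule settled: under three readings the strict-fall case is significant. All of this stands and limits the point.

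It also stands that the objective and hypotheses in the protocol are between groups, and that no document names 6 h against 24 h, or any neighbouring pair, as a question. In the strict-fall case a reader would still see the decline in the Friedman test, in pairs two or more readings apart, and in the reported medians and IQRs. Friedman followed by Nemenyi is a recognised procedure that controls multiplicity.

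What the reply does not remove is the loss of power. The SAP names all within-arm comparisons, and neighbouring pairs are among them. The paired alternative also controls multiplicity, and its result for two readings is computed from those two readings alone.

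**Conclusion.** The concern holds in limited form. With five readings and 20 patients per arm, Nemenyi can have low power for neighbouring readings, and it misses a fall shared by every patient at every step (gap 1.00 against 1.36). How often this would happen depends on the pain course: the 3% to 77% range rests on assumed means and SDs, and the 97% to 100% for the paired tests assumes a within-patient SD of 1.0. The weakness shrinks with early floor scores and under the three-reading schedule. In the strict-fall case, pairs two or more readings apart and the overall Friedman test do not share it. The between-arm analysis is untouched. This is an inexpensive improvement to a secondary analysis and does not threaten the trial's main conclusion.

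**What to change.** In the SAP, keep Friedman as the overall within-arm test and replace the Nemenyi step with: Wilcoxon signed-rank tests of pairs of times within each arm, Holm-adjusted over the pairs in that arm, using every patient with both marks, and reporting the median paired fall with its 95% CI.

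State which reading times are analysed, and reconcile protocol sections 7.8 and 7.9 on this. Using all patients with both marks also avoids the complete-record requirement of the standard Friedman and Nemenyi tests. As an illustration only, if 5% of marks were missing independently, 1 − 0.95⁵ = 23% of patients would drop out of every five-reading within-arm comparison.

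The cost is a sentence or two in the SAP and a few lines of R, with no new data. The SAP is in the past tense. If the analysis has already been run, the signed-rank results should be labelled post hoc and shown beside the Nemenyi results.
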